10.3.2.4 Analysis of the Exploratory Endpoint(S)

Cytokine profile will be described using descriptive statistics, and blood immune response to NSC-CRAd-S-pk7 will be presented as number (percentage) for each category. The association of extent of immune response with overall survival will be determined by Cox's proportional hazards model.

In addition, retroviral testing (RCR testing) will be performed by analyzing patient DNA from whole blood for RCR-specific sequences prior to surgery; at 3 months, 6 months, and 1 year after study treatment; and annually thereafter.

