2.3 Exploratory Objectives & Endpoints

An exploratory objective will be to evaluate cytokine profile and blood immune response to NSC-CRAd-S-pk7 and to determine whether survival rate correlates with extent of immune response.

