3.0 PATIENT ELIGIBILITY

The target population for this study is patients with newly diagnosed malignant glioma. This will be a single-center trial conducted at Northwestern Memorial Hospital and Northwestern Medicine Neurological Surgery clinic of Northwestern University.

Up to 36 subjects will be included in this trial. Approximately 6 potentially eligible patients are seen per month, and it is anticipated that at least 1 per month will be accrued. Potential patients are under the direct care of the Principal Investigator (PI) at Northwestern University, [name] at [contact].

Eligibility will be evaluated by the study team according to the following criteria. Eligibility waivers are not permitted. Subjects must meet all of the inclusion and none of the exclusion criteria to be registered to the study. Study treatment may not begin until a subject is registered. Please refer to Section 11 for complete instructions regarding registration procedures.

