9.0 CORRELATIVES/SPECIAL STUDIES

An exploratory objective will be to evaluate serum cytokine profile and blood immune response to NSC-CRAd-S-pk7 and to determine whether overall survival rate correlates with extent of immune response. In addition, replication competent retrovirus (RCR) testing will be performed by analyzing patient DNA from whole blood for RCR-specific sequences at baseline, 3 months, 6 months, and 1 year after study treatment; and annually thereafter, and to determine whether overall survival rate correlates with persistent gene expression. Real time PCR with 4070A envelope-specific primers will be used to screen DNA extracted from PBMCs from study patients treated with NSCs.

Correlative study (sample type)	Cytokine profile (serum)	Immune response (whole blood)	RCR testing
Mandatory or Optional	Mandatory	Mandatory	Mandatory
Timing (+/- windows)	Baseline, Days 1, 3, 7, 14 and 28 after	Baseline, Days 1, 7, 14 and 28 after study	Baseline, 3 months, 6 months, and 1 year

	study product injection	product injection	after study product injection
Volume Needed (blood only)	4-5 ml	4-5 ml	4-5 ml
Tube type needed (blood only)	EDTA tube	Non-EDTA tube	Non-EDTA tube
Tissue thickness and/or # slides (tissue only)	NA	NA	NA
Processing center	Lurie Research Center (LRC) 3-250	Lurie Research Center (LRC) 3-250	Lurie Research Center (LRC) 3-250
Sample handling/processing instructions	Blood transported directly to LRC within 30 minutes of draw; centrifuge 15 minutes at 3000 rpm; pipette serum into vial and freeze at -80°C until analysis	Blood transported directly to LRC within 30 minutes of draw; freeze at -80°C until analysis	Blood transported directly to LRC within 30 minutes of draw; freeze at -80°C until analysis
Shipping/delivery info	NA	NA	Samples shipped to City of Hope for analysis
Storage needs	Storage available in LRC	Storage available in LRC	Storage available in LRC
Analysis center	LRC	LRC	LRC
Assay methodology	ELISA	ELISA	Real time PCR with 4070A envelope-specific primers

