9.3 Assay Methodology

Cytokine profile and immune response samples will be analyzed using enzyme-linked immunosorbent spot (ELISA). RCR samples will be analyzed using real time PCR with 4070A envelope-specific primers.

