10.2 Sample Size and Accrual

This phase 1 study is not powered to detect statistically significant differences in efficacy. The primary endpoint of this Phase I dose-escalation study is the MTD of NSC-CRAd-S-pk7 when administered with standard radiation and chemotherapy in patients with malignant glioma. The 3+3 design has a 71% chance (49%, 17%) of dose escalating when the true toxicity rate for that dose is 20% (30%, 50%).

If all three dose levels are administered, the minimum number of patients enrolled will be 9 per arm and the maximum number of patients will be 18 per arm, for total accrual of 18-36 patients enrolled. Based upon the dose escalation schema described, groups of three to six patients will be entered at a dose level in each arm. Using this algorithm, the probabilities of dose escalation for various true DLT rates are given in Table 10. For example, if the true DLT is 50% at a dose level, there is a 17% chance that the dose would be escalated. The maximum tolerated dose determined in this study will be the recommended dose for a Phase II study. In the event the final pathology reading reveals anything other than a malignant glioma, such a patient will not be counted as one of the minimum number required without DLT for advancement to the next dose level but will be counted if a DLT is experienced.

Table 10– Probabilities of Dose Escalation	
20%	71%
30%	49%
40%	31%
50%	17%
60%	8%

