10.3.2 Description of Statistical Methods

10.3.2.1 General Approach

All study data will be presented in by-subject data listings. Statistical analysis will be descriptive only, with no hypothesis testing. All the endpoint data will be collected and described in summary tables for both two arms at each dose. In general, descriptive statistics (n, mean, standard deviation, median, minimum, and maximum) will be presented for continuous variables. Frequencies and percentages will be calculated for categorical and ordinal variables at each category. Statistical analyses will be performed using SAS9.4 (SAS Institute Inc., Cary, NC)

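### Blood immune response is planned only as counts in undefined categories, and the Cox model relating its extent to survival states no covariate scale or time point

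*Combined protocol and SAP*

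**What the plan says.** The exploratory objective (Section 2.3) is "to determine whether survival rate correlates with extent of immune response". Section 10.3.2.4 handles it in two separate sentences.

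- Presentation: "blood immune response to NSC-CRAd-S-pk7 will be presented as number (percentage) for each category". The same sentence gives the cytokine profile descriptive statistics.
- Association: "The association of extent of immune response with overall survival will be determined by Cox's proportional hazards model".

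Sections 6.3, 9.0 and 10.3.2.4 define no category, cut or responder rule. Section 9.3 states: "Cytokine profile and immune response samples will be analyzed using enzyme-linked immunosorbent spot (ELISA". The table in Section 9.0 lists ELISA for both measures. No analyte, unit or readout scale is given.

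That table gives the immune-response sampling times as "Baseline, Days 1, 7, 14 and 28 after study" product injection. Table 4 instead describes draws that may be taken in week 2-3 and again 2-4 weeks after radiotherapy. Neither place says which sample measures the extent of response.

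Section 10.3.2.1 states: "Statistical analysis will be descriptive only, with no hypothesis testing". It assigns mean, SD, median and range to continuous variables, and frequencies and percentages to categorical and ordinal ones. Section 10.3 defers further detail to a formal SAP, to be completed before database lock. Section 3.0 states: "Up to 36 subjects will be included in this trial".

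**The concern.** Extent is a graded quantity, but the only summary the plan gives for it is a count per category. Under the plan's own convention in Section 10.3.2.1, that treats the immune response as categorical, while the cytokine profile is treated as continuous. No reason is given for the difference.

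Two things are at stake.

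- **Precision.** If the categories are carried into the Cox model, an analysis that already has at most 36 patients uses only part of what the assay measured.
- **Freedom of choice.** With no cut and no day fixed, both can be picked after survival is known. The trial is open label, and deaths will accrue well before database lock, so a SAP finished just before lock would not prevent this. A hazard ratio from a cut chosen that way overstates the association.

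**Working it through.** **Inputs from the documents.** Three dose levels, 3 to 6 patients per level, two arms (Sections 4.2 and 10.2). Minimum 3 × 3 × 2 = 18 and maximum 3 × 6 × 2 = 36, which reproduces "for total accrual of 18-36 patients enrolled". The plan states no figure for the immune-response analysis itself.

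**Assumptions, because the plan gives none.** A normally distributed marker (on a log scale if necessary), a small log-hazard slope, and groupings from a 10/90 split to five equal groups.

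**Information kept after grouping.** This is the between-group share of the marker's variance, Σ P_k·m_k². P_k is the probability of group k and m_k = (φ(a) − φ(b))/P_k is the marker mean between its limits a and b.

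- Median split: m = ±0.3989/0.5 = ±0.798, and 0.798² = 0.637. Loss 36.3%.
- 10/90 split: m = −1.755 and 0.195, so 0.1 × 3.080 + 0.9 × 0.038 = 0.342. Loss 65.8%.
- Five equal groups: m = ±1.400, ±0.532 and 0, so 0.4 × (1.960 + 0.283) = 0.897. Loss 10.3%.

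| Covariate | Information kept | Loss | Effective N of 36 |
|---|---|---|---|
| Continuous | 1.000 | 0% | 36.0 |
| Five equal groups | 0.897 | 10.3% | 32.3 |
| Four equal groups | 0.861 | 13.9% | 31.0 |
| Three equal groups | 0.793 | 20.7% | 28.6 |
| Median split | 0.637 | 36.3% | 22.9 |
| 30/70 split | 0.576 | 42.4% | 20.7 |
| 20/80 split | 0.490 | 51.0% | 17.6 |
| 10/90 split | 0.342 | 65.8% | 12.3 |

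**Meaning for the interval.** The analysis is descriptive, so interval width is a better yardstick than power. On the per-SD scale the 95% limits are approximately the hazard ratio divided and multiplied by exp(1.96/√(D × information kept)), where D is the number of deaths. Taking D = 36, which is the best case and an assumption:

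- continuous: exp(1.96/√36) = 1.39
- five equal groups: exp(1.96/√32.3) = 1.41
- median split: exp(1.96/√22.9) = 1.51
- 10/90 split: exp(1.96/√12.3) = 1.75

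For an assumed hazard ratio of 1.5 per SD, the interval is about 1.08 to 2.08 with the continuous covariate and about 1.00 to 2.26 with a median split.

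**Choosing the cut afterwards.** I simulated 4,000 trials at each of 18, 24 and 36 patients (assumed 15, 20 and 30 deaths), with no true association and the most favourable cut between the 20th and 80th percentiles chosen after seeing survival. Nominal p < 0.05 occurred in about 29% to 31% of trials. A continuous covariate fixed in advance gave 5% to 6%. The test is only a yardstick for how far such a choice distorts the estimate.

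**The case against.** A reader might infer that the plan categorises the response before relating it to survival, and so discards about a third of the information. The documents do not support that. The category sentence concerns presentation, the Cox sentence is separate, and nothing makes the categories its covariate. The word extent fits a graded value at least as well, and with a continuous covariate the loss is zero. The one-third figure also needs a two-group split near the median of a normal marker, and the plan gives neither a number of groups nor a cut. This part of the objection stands, and the losses above are therefore conditional.

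Three further points have some force.

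- The readout scale is inferred from the assay name. The documents do not state it.
- All data go into by-subject listings and more analysis detail is deferred to the SAP. Listings do not define the covariate, however, and a deadline of database lock does not come before survival is known in an open-label trial.
- The analysis is exploratory, with no hypothesis testing and no powering for efficacy. This limits the consequence. It does not remove it, since Section 10.3.2.4 still commits to a Cox model whose hazard ratio will be read.

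**Conclusion.** The point holds as a conditional one. Section 10.3.2.4 gives the immune response a categorical summary with undefined categories, and leaves the scale and day of the Cox covariate open. A continuous form specified in advance answers the stated question better at almost no cost.

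The loss is about 10% to 66% over the groupings considered, 36% for a median split, and nil if the covariate is continuous. It rests on a normal marker, a small slope, a quantitative assay readout and the assumed groupings. The plan does not establish any particular loss, a third included. The undefined cut and day are the firmer part of the concern, because they follow from the text without assuming a grouping. Severity is low: the endpoint is exploratory and the analysis descriptive.

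**What to change.** Amend Section 10.3.2.4, and carry the wording into the SAP before survival data are linked to the immune data.

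- Confirm that the assay readout is quantitative and state its unit. Summarise it at each sampling time as a continuous value (n, median, quartiles, individual profiles).
- Name one primary post-injection day in advance, from a sampling schedule on which Section 9.0 and Table 4 agree.
- Enter the log change from baseline at that day as a continuous Cox covariate, with a stated rule for zero or undetectable values.
- Count survival from that day (landmark). Section 6.2 starts overall survival at injection and Section 10.3.2.3 at study inclusion. Both precede a post-injection sample, so a patient must survive to be measured.
- Report the hazard ratio with its 95% confidence interval, labelled as descriptive.
- Keep any responder category for display only, with its cut fixed before survival data are linked.

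The cost is wording: no added blood draws, assays or patients. There are two downsides. The model assumes log-linearity, which a residual plot can check only weakly in 18 to 36 patients. Patients who die before the landmark day, or lack a baseline or landmark sample, drop out of this analysis, and their number should be reported.

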4.1 Overview

This study is an open label, Phase I, dose-escalation gene therapy clinical trial with two arms:

1. **Arm A** – Unresectable disease, will receive stereotactic intratumoral injection of NSC-CRAd-S-pk7 immediately following stereotactic biopsy confirmation of clinical diagnosis
2. **Arm B** – Resectable or partially resectable disease, will receive injection of NSC-CRAd-S-pk7 into remaining tumor or tumor bed after resection.

Pathologic confirmation of a malignant glioma must be made at the time of surgery prior to injection. If this is not possible, the injection will not be performed and the patient will no longer be eligible for the study. In the event that the final pathology reading reveals anything other than a malignant glioma, the patient will be removed from the protocol but will continue to be followed for toxicity. Patients having not received any study treatment will need to be replaced and will not be counted as one of the minimum number required without DLT for advancement to the next dose level but will be counted if a DLT is experienced.

Standard radiotherapy and chemotherapy will begin 10-14 days after NSC-CRAd-S-pk7 injection. Long-term follow-up of general health status and any side effects may continue for life. This will be done by telephone contact or letter with the patient or their primary care physician. Medical records will also be reviewed to assess for any potential side effects and for general health status.

An attempt will be made to perform a complete autopsy on any patient who dies, if consent is given by the legally authorized representative. In addition to standard pathological examinations, tissues will be taken for additional studies such as analysis of CRAd-S-pk7 presence and expression.

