10.3.1 Analysis Datasets

All the analysis will be conducted in the safety population, including all the patients who received at least one dose of NSC-CRAd-S-pk7.

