10.3.2.3 Analysis of the Secondary Endpoint(S)

For objective tumor response, a summary table will be produced to present the number and proportion of responders in each arm, together with each of the response categories, namely CR, PR, MR, SD, P and PP.

The analysis of overall survival and progression-free survival are based on the survival function, estimated by the Kaplan-Meier method. Survival will be calculated from the day of study inclusion until progression and death, respectively, or will be censored at the date of last available follow-up information. The survival function will be summarized for 25th percentile, median, and 75th percentile, and the survival curves of the two arms will be presented.

Descriptive statistics will be used to describe the overall quality-of-life score on physical well-being, social/family well-being, emotional well-being, functional well-being and additional concerns, respectively.

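### The Cox model of overall survival on immune response is specified without stratification or adjustment by arm, so its descriptive hazard ratio can mix the effect of resectability with the immune association, in either direction

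*Combined protocol and SAP*

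**What the plan says.** The analysis is one sentence in Section 10.3.2.4, repeated in the synopsis under Statistical Considerations: "The association of extent of immune response with overall survival will be determined by Cox's proportional hazards model". Extent of immune response is the only term named. No stratum, arm term or other covariate is given.

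On the population, Section 10.3.1 states: "All the analysis will be conducted in the safety population". That population is everyone injected, in both arms.

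Section 4.1 defines the arms by resectability. Arm A is "Unresectable disease, will receive stereotactic intratumoral injection of NSC-CRAd-S-pk7". Arm B is "Resectable or partially resectable disease, will receive injection of NSC-CRAd-S-pk7 into remaining tumor or tumor bed after resection". On size, Section 10.2 says that if all three dose levels are used "the minimum number of patients enrolled will be 9 per arm and the maximum number of patients will be 18 per arm".

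Elsewhere the plan does separate the arms. For overall and progression-free survival, Section 10.3.2.3 says "the survival curves of the two arms will be presented", and Section 10.3.2.1 puts endpoint summaries in tables by arm and dose. Neither statement covers the Cox model. Section 10.3.2.1 also says: "Statistical analysis will be descriptive only, with no hypothesis testing". Section 10.3 defers further detail to a formal SAP due before database lock.

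**The concern.** Arm is a patient characteristic here, not an assigned treatment. It could be related to both sides of the regression. Resectability may go with survival. The procedures in Section 4.4 also differ: needle biopsy and infusion at one to three tumor sites in Arm A, against craniotomy and up to ten cavity-wall injections in Arm B. That could affect a blood immune readout taken from day 1 to day 28 (Section 9.0). Doses escalate independently by arm (Section 4.2), so the dose mix may differ as well.

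If both links exist, a pooled one-covariate fit credits part of the arm's survival difference to the immune response. Whether survival correlates with the extent of that response is a stated exploratory objective (Section 2.3), and this regression is what the plan offers to answer it. A distorted HR could suggest an immune benefit or harm that is not there, or hide one that is.

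**Working it through.** **No plan figure to reproduce.** The documents give no events, effect size or power for this model. Table 10 concerns 3+3 escalation only. It does reproduce (at a true DLT rate of 50%: 0.5³ + 3 × 0.5 × 0.5² × 0.5³ = 0.172, stated as 17%), but it does not bear on this point.

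**Inputs from the documents.** 9 to 18 patients per arm (Section 10.2). Survival follow-up of up to 5 years, taken as 60 months (Section 4.9). Median survival of 12 to 15 months with standard therapy, for scale (Section 1.1).

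**Assumptions.** Exponential survival. Immune response coded as high or low, since the plan does not define its extent. True immune HR of 1.0. H is the hazard in Arm A divided by that in Arm B, set at 1.5, 2 or 3. Responder shares are varied. The documents give neither survival by resectability nor immune response by arm.

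**Hand check.** With equal arms and responders 30% in A and 70% in B, responders are 30% A and 70% B, and non-responders the reverse. With no immune effect, the responder to non-responder hazard ratio at time zero is

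R = (0.30 H + 0.70) / (0.70 H + 0.30).

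**Simulation.** This carries the comparison over the whole follow-up, with a Cox fit pooled and then stratified by arm. At 18 per arm:

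| Responders A / B | H | R by hand | Pooled HR | Stratified HR |
|---|---|---|---|---|
| 30% / 70% | 1.5 | 1.15/1.35 = 0.85 | 0.84 | about 1.0 |
| 30% / 70% | 2 | 1.30/1.70 = 0.76 | 0.75 | about 1.0 |
| 30% / 70% | 3 | 1.60/2.40 = 0.67 | 0.68 | about 1.0 |
| 40% / 60% | 2 | 1.40/1.60 = 0.88 | 0.87 | about 1.0 |
| 70% / 30% | 2 | 1.70/1.30 = 1.31 | about 1.3 | about 1.0 |
| equal shares | any | 1.00 | about 1.0 | about 1.0 |
| any | 1 | 1.00 | about 1.0 | about 1.0 |

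The bias hardly depends on sample size: at 9 per arm, H = 2 and 30% vs 70%, the pooled HR is again 0.75. It can also mask a real association. With a true immune HR of 0.5, H = 2 and responders 70% vs 30%, the pooled estimate is 0.68 and the stratified one 0.51.

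**Which H is plausible.** Under exponential survival H is the ratio of medians. With 15 months in the better arm, H = 1.5 puts the other at 10 months, H = 2 at 7.5 and H = 3 at 5. The lowest median in Section 1.1 is 10 months (GBM with conventional radiation). None of its figures is by resectability, but they lend more support to H near 1.5 than to 2 or 3.

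**Precision.** The standard error (SE) of the log HR rises as follows:

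| Per arm | Pooled | Stratified, equal shares | Stratified, 30% / 70% |
|---|---|---|---|
| 18 | about 0.35 | 0.37 | 0.40 |
| 9 | about 0.52 | 0.56 | 0.62 |

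As 95% limits under 30% vs 70%, the HR is multiplied and divided by exp(1.96 × 0.35) = 1.99 pooled and exp(1.96 × 0.40) = 2.19 stratified at 18 per arm. At 9 per arm the factors are 2.77 and 3.37.

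**The case against.** A reader might infer more than the documents support.

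- **That the plan prescribes an unstratified test.** It does neither. It is silent on arm, a fuller SAP is promised, and hypothesis testing is ruled out. False-positive rates and power are therefore the wrong yardstick; what is at issue is bias in a descriptive HR. The silence still matters. The literal reading is a one-covariate pooled fit, and in an open-label trial results by arm may be visible before the later SAP settles the model.
- **That the bias makes immune response look protective.** This needs longer survival and more responders in the same arm. With the opposite pattern it points to harm, and if either difference is absent there is none. The documents report neither.
- **That this is the only analysis of the exploratory objective.** Cytokine profile and immune response are also summarised descriptively. Tables by arm and dose, with by-subject listings, would let a reader see an imbalance in responders. They would not correct the HR.
- **That stratifying is free.** It is not. Take ln(pooled HR) as the bias and combine it with the SE as a root mean square. Under 30% vs 70% at 18 per arm, the pooled error is √(0.174² + 0.35²) = 0.39 at H = 1.5 and √(0.288² + 0.35²) = 0.45 at H = 2, against 0.40 stratified. At 9 per arm it is √(0.174² + 0.52²) = 0.55 and √(0.288² + 0.52²) = 0.59, against 0.62. So with 9 per arm and H of 1.5 or 2, stratifying loses slightly more precision than the bias it removes.

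The last point stands as a real cost. It does not rescue the pooled fit as an answer to the stated question: its interval is narrower but centred on a mixture, whereas the stratified interval is wider and shows how little the data say.

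**Conclusion.** The point holds in limited form. As written, the model takes no account of arm, and arm is non-randomised and defined by resectability. When survival and responder frequency both differ by arm, the pooled HR is biased in a direction that cannot be known in advance. Under a responder split of 30% vs 70%, a true HR of 1.0 would be reported as about 0.84 at an arm hazard ratio of 1.5, and about 0.75 or 0.68 at the less supported ratios of 2 and 3. Reversing the split at a ratio of 2 gives about 1.3. These figures rest on assumed arm differences, a binary immune measure and exponential survival.

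At 18 per arm, the shift at a ratio of 1.5 is about half a standard error (0.174/0.35 = 0.50). It could colour the interpretation of an exploratory estimate that will be imprecise in any case. It does not touch the dose-escalation decisions or the MTD. Label: cheap improvement.

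**What to change.** In Section 10.3.2.4 and the synopsis, state that the Cox model of overall survival on extent of immune response is stratified by arm. Report the HR with its confidence interval as exploratory and descriptive, and show the estimate within each arm beside it.

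The change is one line of text and a STRATA statement in SAS, with no new data. The price is precision: the log-HR SE rises from about 0.35 to 0.37–0.40 at 18 per arm and from about 0.52 to 0.56–0.62 at 9 per arm, more when responder shares differ by arm. Per-arm estimates from 9 to 18 patients will be very wide and should be presented as such. Stratifying by arm does not deal with dose differences within an arm, and it does not define extent of immune response; the formal SAP would need to address both separately.
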